## Primary Dependent Variable

**NSSI Frequency in the Past 3 Months.** Our primary outcome variable will compare past 3-month NSSI frequency at 3-month follow-up—for participants assigned to the Project SAVE SSI versus supportive therapy SSI (i.e. control condition). At pre-intervention and 3-month follow-up time points, participants will indicate "how many times they have purposely hurt themselves without wanting to die" in the past 3 months in an open-response text box. Notably, in the present study's survey flow, this question is displayed following display logic—such that

participants endorsing zero NSSI in the past 3-months (via a previous question) skip to the end of the question block and are not prompted to answer our main frequency outcome question. For these individuals, we will impute a past 3-month frequency value equal to 0 (as they have endorsed zero NSSI in the previous 3 months in the earlier question). More information about how we will handle very large numbers (i.e. outliers) for this outcome is reported below (see “Outliers and Exclusions” section; “Winsorizing Outliers” subsection).

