between conditions in the present study, we will report the results of our main analyses below, highlighting (1) limitations to interpretation, and (2) ways in which this will inform future intervention development.

Further, if unequal dropout is present, we will run a sensitivity analysis to determine a range of possible effect sizes for our outcomes of interest, varying how much “dropout participants” may have changed on each outcome. To establish lower- and upper-end estimates of effect size, we will: (1) calculate residual change for each of our 3 outcomes, (2) identify the 25th and 75th percentile values for residual change in each outcome, (3) run analyses for each outcome where we impute the lower residual change value (25th percentile) for all dropouts/missing data, as well as the higher residual change value (75th percentile) for all dropouts/missing data. This approach explicitly assumes data are not missing at random, providing a more unbiased estimate of the overall treatment effect in the presence of unequal dropout.

***Testing Hypothesis 1: Do teenagers in the Project SAVE SSI condition report lower self-reported likelihood of future NSSI immediately post-intervention—relative to teenagers in the active control program?***

We will first test if the assumptions necessary to interpret a multiple linear regression are met. If not, we will follow the procedures below. We will document any of these changes when we report our results.

- If assumptions for interpreting a multiple linear regression *are not* met, we will perform a two-way ordinal regression (as this outcome will be Likert data), with pre-intervention likelihood of future NSSI and treatment condition entered as our independent variables, and post-intervention likelihood of future NSSI as the dependent variable. We will consider a p value of less than .05 for treatment condition (in favor of the Project SAVE SSI) as a significant effect of the Project SAVE treatment on likelihood of future NSSI.
- If the assumptions for interpreting a multiple linear regression *are* met, we will enter pre-intervention likelihood of future NSSI as a covariate and treatment condition as the predictor of post-intervention likelihood of future NSSI in a multiple linear regression. We will consider a p value of less than .05 for the treatment condition coefficient (in favor of the Project SAVE SSI) as a significant effect of the Project SAVE treatment on likelihood of future NSSI.

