***Testing Hypothesis 2: Do teenagers in the Project SAVE SSI condition endorse lower frequency of SI in the past 3 months—relative to teenagers in the active control program?***

First, we create our secondary outcome variable (i.e. frequency of SI in the past 3 months) by imputing values equal to 0 for participants who endorsed zero SI in the previous 3 months in an earlier question. See “SI Frequency in the Past 3 Months” under the key dependent variables section for more details.

Next, we will determine whether a Poisson regression, a negative binomial regression, a zero-inflated Poisson regression, or a zero-inflated negative binomial regression is most appropriate for analyzing our past 3-month frequency outcome (count variable). To do this, we will run all four models, conducting model fit tests to compare AIC values, BIC values, and raw scores for each regression. If all three indices agree (i.e. select the same “best” model of the four possible), we will interpret the results of that regression. If they do not agree (i.e. select different “best” models from the four possible), we will report the results from each of the selected models.

Regardless of model type, we will enter pre-intervention past 3-month frequency of SI as a covariate, and treatment condition as a predictor, of past 3-month frequency of SI at follow-up in the chosen regression(s). We will consider a *p* value of less than .05 for the treatment condition coefficient (in favor of the Project SAVE SSI) as a significant effect of the Project SAVE treatment on frequency of SI in the past 3-months.

***Testing Hypothesis 3: Do teenagers in the Project SAVE SSI condition endorse lower frequency of NSSI in the past 3 months—relative to teenagers in the active control program?***

We will follow the same procedures for hypothesis 2 but replacing “SI frequency in the past 3 months” with “NSSI frequency in the past 3 months.”

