### ***Type 1 Exclusions***

Type 1 exclusions are exclusions that can be automated and do not require consensus among investigators. A research team member who will not be involved with conducting the primary study analyses will use type 1 exclusions to determine when participant recruitment is complete. Recruitment for the present study will end once 500 participants have been randomized *who pass all type 1 exclusions tests* (i.e. are still eligible for inclusion after excluding for type 1 criteria; see our section on sample size for more details).

Here, we will exclude participants that fail to meet the following study inclusion criteria:

- Must be 13 - 16 years old at the time of the baseline survey
- Must report comfort reading and writing in English

- Must endorse no learning disability, visual impairment, or other difficulty that makes it difficult to answer questions on a computer
- Must have access to a laptop or smartphone with internet access
- Must endorse purposefully hurting self without wanting to die within the past month
- Must endorse *either* “I do not like myself” or “I hate myself” on CDI-II item 7 in a screener survey

Here, we will exclude the following participants based on failure to meet the following quality check criteria:

- Participants who exit the study *prior* to condition randomization for our listed analyses (note: the present study will use an intention-to-treat approach, where every participant who was randomized to a study condition—and who is not excluded for one of the specific reasons outlined in this section—will be included in our analyses)

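### The primary test names no deciding model when the fit indices disagree, and no deciding treatment coefficient when the model is zero-inflated

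*Combined protocol and SAP*

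**What the plan says.** The procedure is written under Testing Hypothesis 2. Testing Hypothesis 3, the primary outcome, takes it over: "We will follow the same procedures for hypothesis 2", with NSSI frequency in place of SI frequency. The section Primary Dependent Variable frames the question as one of frequency: "Our primary outcome variable will compare past 3-month NSSI frequency at 3-month follow-up" between the two arms.

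- **Candidates.** Poisson, negative binomial (NB), zero-inflated Poisson and zero-inflated negative binomial (ZINB).
- **Selection.** All four are fitted, "conducting model fit tests to compare AIC values, BIC values, and raw scores for each regression". If the three indices pick the same model, that model is interpreted. If not, "we will report the results from each of the selected models".
- **Terms.** Baseline frequency and condition, whatever the model type. The zero part of a zero-inflated model is not mentioned.
- **Success.** A p "value of less than .05 for the treatment condition coefficient (in favor of the Project SAVE SSI"), in the singular, after a false discovery rate (FDR) correction across Hypotheses 1 to 3 (Correcting for Multiple Comparisons).

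Hypothesis 1 is handled differently. If the linear-model assumptions fail, "we will perform a two-way ordinal regression (as this outcome will be Likert data"); each branch leads to one model and one treatment test.

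Imputing Data creates several imputed datasets and then repeats all tests on the non-imputed data. It does not say whether the count model is selected once or afresh each time. Treatment Effects Among SSI Completers reuses the Hypothesis 3 procedure.

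**The concern.** Four things are missing from the rule that decides the primary outcome.

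1. The third index is undefined, yet all three must agree before a single model is interpreted.
2. When they disagree, reporting several models does not say whether the hypothesis is supported. The FDR step needs one p-value per hypothesis, and Hypothesis 3 then has none designated.
3. A zero-inflated model with condition in both parts has two treatment coefficients. The likeliest reading is that the count coefficient decides. That coefficient describes a latent class that is not always zero, whereas the stated question is about overall frequency. Type 1 Exclusions sets the entry rule "Must endorse purposefully hurting self without wanting to die within the past month", so a zero at follow-up is a youth who had been self-injuring and now reports none for three months. A benefit through stopping would sit mainly in the zero part.
4. If selection is repeated in each imputed dataset and again in the non-imputed data, the promised comparison of the two analyses can differ through model choice alone.

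What is at stake is whether the primary verdict is determined, and whether it answers the stated question. Type I error is not the main issue.

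**Working it through.** **Inputs from the documents.** N = 500, 250 per arm (2 × 250 = 500); four models; baseline and condition as terms; winsorizing at the 95th percentile. The plan gives no power, mean count, dispersion or proportion of zeros, so there is no planned figure to reproduce and every simulated rate rests on assumptions.

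**1. When AIC and BIC must split.** With baseline and arm in both parts (an assumption, since the plan is silent), ZINB has 3 + 3 + 1 = 7 parameters and NB has 3 + 1 = 4, a difference of 3. Let G be twice the log-likelihood gain of ZINB over NB.
- AIC picks ZINB if G > 2 × 3 = 6.
- BIC picks ZINB if G > 3 × ln(500) = 18.64 (17.97 at N = 400).
- Any G in between splits them. With an intercept-only zero part the band is 2 to ln(500) = 6.21.

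**2. The third index.** If it means the maximised log-likelihood, ZINB contains the other three models and cannot lose to them. Poisson or NB could then never be the agreed model.

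**3. What each coefficient measures.** With structural-zero proportion π and count mean μ, overall mean frequency is (1 − π)μ, so the SAVE/control ratio is [(1 − π₁)μ₁] / [(1 − π₀)μ₀]. The count coefficient captures only μ₁/μ₀. For zeros of 20% versus 40% and equal μ, the overall ratio is 0.60/0.80 = 0.75 while the count ratio is 1.

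**4. Simulations (250 per arm, winsorized counts, baseline and arm in both parts).**
- *A:* 300 runs per cell (Monte Carlo SE at most 2.9 points); NB dispersion/mean 0.5/5, 0.7/10 and 1.0/20; baseline at least 1; follow-up mean proportional to the square root of baseline; baseline entered unlogged.
- *B:* 1,000 runs per cell; mean about 8 outside the structural zeros; NB size 0.6 or 1; follow-up log-linear in baseline; third index read as log-likelihood.

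Index disagreement:
- *A, AIC versus BIC:* 41–55% with no zero inflation (13–36% with an intercept-only zero part), 72% with 10% (0.7/10 only), 0–72% with 20%.
- *B, all three indices:* 99.4% with no structural zeros, 13.4% with 15%, 0.1% with 30%. Log-likelihood picked ZINB in 99.9–100%. With no structural zeros AIC picked ZINB in 35% and BIC in 0.5%, so those two split in 35 − 0.5 = 34.5%.

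Trials favouring SAVE at two-sided p < .05, before FDR:

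| Assumed effect | Implied overall ratio | ZINB count part | ZINB zero part | Overall ratio (A) or NB coefficient (B) |
|---|---|---|---|---|
| A: zeros 20% vs 30% | 0.70/0.80 = 0.875 | 1–2% | 24–59% | 14–21% |
| A: zeros 20% vs 40% | 0.75 | 1–2% | 81–99% | 44–65% |
| A: zeros 20% vs 30%, counts 15% lower (0.7/10 only) | 0.875 × 0.85 = 0.744 | 14% | 50% | 56% |
| B: zeros 20% vs 32% | 0.68/0.80 = 0.85 | 2.1% | 67.9% | 17.0% |
| B: count ratio 0.75, zeros 20% in both | 0.75 | 62.0% | 3.4% | 48.8% |

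In the two B rows, coefficients from the selected models gave conflicting verdicts in 67.4% and 62.9% of trials, although the indices seldom disagreed. In A, under a uniform 25% reduction, NB and the ZINB count coefficient were both reported with opposite verdicts in 2–15% of runs at .05. At .0167 (.05/3, the strictest Benjamini–Hochberg threshold for three tests) the figure was 4–8%.

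**5. Selection across imputed datasets.** This used 150 runs per cell at 0.7/10, an assumed 20% missing at random, and 20 imputations approximating the plan's method.

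| Cell | Not unanimous, AIC | Not unanimous, BIC | Observed-data choice differs from imputed majority, AIC | Same, BIC |
|---|---|---|---|---|
| Null, no zero inflation | 62% | 13% | 16% | 0% |
| Null, 10% zeros | 65% | 23% | 15% | 8% |
| Uniform 25% reduction | 61% | 14% | 17% | 1% |
| Zeros 20% vs 40% | 1% | 57% | 0% | 15% |

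**6. False positives.** If any reported coefficient counted, the null rate favouring SAVE was 2–6% in A and 3.5–5.1% in B, against a nominal 2.5%. The excess is modest, and the plan does not say that one significant model suffices.

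**The case against.** The plan fixes the four models, the indices and the favourable direction in advance, and commits to reporting every selected model, which limits selective reporting. It describes condition as a predictor of frequency and refers to one coefficient, so the count coefficient can fairly be inferred. On that reading, what remains is one missing clause and a preference about the estimand.

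The argument about stopping needs structural zeros that differ by arm. The entry criterion shows self-injury before baseline; it does not show that follow-up zeros will exceed what an NB model predicts. The disagreement rates depend on the assumed design. At 0.7/10 with no zero inflation, removing the baseline misfit lowered the AIC/BIC split from 53% to 36% (log-linear truth) or 25% (logged baseline), although at 0.5/5 it stayed at 47–55% (150 runs per cell, SE about 4 points). 'Raw scores' may mean something other than log-likelihood. Index disagreement need not change the verdict. The overall ratio also has less power than a zero-part test when benefit comes through stopping.

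Much of this stands as a limit on the size. It does not supply a deciding model, a definition of the third index or a single p-value for the FDR step, and no other section does. The inferred count coefficient is also the one that misses a benefit through stopping.

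**Conclusion.** The concern holds and should be settled before the data are seen by arm. Followed exactly, the rule can leave the primary hypothesis without a designated result, and the same applies to the SI hypothesis and the completer analysis.

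The gaps in the text, and the bands for a given zero-part specification, need no assumed count distribution. The bands do assume that NB and ZINB are the contenders and depend on N. How often the indices split is not established: the simulated AIC/BIC figures run from 0% to 72% with the assumed shape, the zero proportion and the form of the baseline term.

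The coefficient problem is separate and arises even when all indices agree on a zero-inflated model. Both simulations show the same direction: an effect confined to the zeros is nearly invisible to the count coefficient (1–2% in A, 2.1% in B). A further 120-run check with zeros of 20% versus 40% gave about 4–6% by the count part and 88–96% by the zero part.

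**What to change.** Before any outcome is examined by arm:

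1. Drop 'raw scores' and name one deciding index, for example BIC.
2. Select the model once, and use it in every imputed dataset and in the non-imputed re-run.
3. State that selection is made without the arm term, because the section on conditions lifts investigator masking at the analysis phase.
4. State which terms enter the zero part, and name one deciding treatment test per hypothesis that reflects overall frequency. One suitable option is the SAVE/control ratio of mean 3-month frequency, zero and count parts combined, standardised over baseline, with a robust or bootstrap standard error.
5. Enter only that p-value for each hypothesis in the FDR step, three in total.
6. Report the other models, and the separate zero and count coefficients, as sensitivity or supportive results.

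The cost is a few sentences and a short standardisation step in the code, with no new data. The drawback is lower power than a zero-part test if SAVE works mainly by stopping self-injury (14–21% against 24–59% for zeros of 20% versus 30%; 44–65% against 81–99% for 20% versus 40%), which is why the zero part should be a named supportive result. Under a uniform 25% reduction without zero inflation, the overall ratio matches the NB coefficient with the same robust standard error (46–79% against 46–80%).

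Run with imputation under the assumptions in step 5 of the working (SE at most 4.1 points), this fix gave two-sided null rates of 1.3% (no zero inflation) and 4.7% (10%). Power was 52% for the uniform reduction and 53% for zeros of 20% versus 40%.

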### ***Correcting for Multiple Comparisons***

We will use a false discovery rate approach to correct for multiple comparisons among our main confirmatory tests of hypotheses 1 - 3. As such, in all places where a significant effect is defined by a *p* value less than .05, this is referring to the post-correction *p* value (i.e. the *p* value after correction using the false discovery rate method).

***Outliers and Exclusions. Describe exactly how outliers will be defined and handled, and your precise rule(s) for excluding observations. (optional)***

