## What's the main question being asked or hypothesis being tested in this study?

To determine whether participants randomized to an online single session intervention (SSI) targeting non-suicidal self-injurious behavior ("Project SAVE") endorse:

1. Lower self-reported *likelihood* of future non-suicidal self injury immediately post-intervention (secondary outcome)
2. Lower self-reported *frequency* of suicidal ideation (in the past 3 months) at 3 month follow-up (secondary outcome)
3. Lower self-reported *frequency* of non-suicidal self-injury (in the past 3 months) at 3 month follow-up (primary outcome)

relative to those randomized to an active control condition (i.e. supportive therapy SSI; Schleider & Weisz, 2018) in a large sample of cisgender heterosexual & sexual and gender minority teenagers ages 13-16 years old.

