### ***Secondary Dependent Variables***

**Likelihood of Future NSSI.** Likelihood of future NSSI will be measured immediately pre- and post-intervention. We will evaluate self-reported likelihood of future non-suicidal self-injury immediately post-intervention—comparing participants in the Project SAVE SSI versus supportive therapy SSI control conditions, and controlling for pre-intervention likelihood score. An item from the Self-Injurious Thoughts and Behaviors Interview-R (Fox et al., 2020) will assess participants’ beliefs about the likelihood of future non-suicidal self injury on a 5-point Likert Scale (range = 0 to 4; 0 = “not at all”; 4 = “extremely”).

**SI Frequency in the Past 3 Months.** We will compare past 3-month SI frequency at 3-month follow-up—for participants assigned to the Project SAVE SSI versus supportive therapy SSI (i.e. control condition). At pre-intervention and 3-month follow-up time points, participants will indicate “how many days did they have thoughts about killing themselves for more than a few minutes” in the past 3 months in an open-response text box. Notably, in the present study’s survey flow, this question is displayed following display logic—such that participants endorsing zero history of SI in the past 3 months (via a previous question) skip to the end of the question block and are not prompted to answer our frequency outcome question. For these individuals, we will impute a past 3-month frequency value equal to 0 (as they have endorsed zero SI in the previous 3 months in the earlier question). More information about how we will handle very large numbers (i.e. outliers) for this outcome is reported below (see “Outliers and Exclusions” section; “Winsorizing Outliers” subsection).

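### The only primary outcome (H3) shares one FDR family with two secondary outcomes, so its verdict depends on their p values: valid and conservative, but cheap to improve

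*Combined protocol and SAP*

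**What the plan says.** The section on the main question lists three hypotheses and labels each. H3 is the frequency "of non-suicidal self-injury (in the past 3 months) at 3 month follow-up (primary outcome"), and it is the only one labelled primary. H1 is the likelihood of "future non-suicidal self injury immediately post-intervention (secondary outcome"). H2, suicidal ideation frequency at the same follow-up as H3, is also labelled secondary. The section Secondary Dependent Variables fixes the timing of H1: "Likelihood of future NSSI will be measured immediately pre- and post-intervention".

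The section Correcting for Multiple Comparisons uses a false discovery rate method to "correct for multiple comparisons among our main confirmatory tests of hypotheses 1 - 3". It adds that wherever significance is defined by a p "value less than .05, this is referring to the post-correction" p value. The particular FDR procedure is not named.

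Testing Hypothesis 3 takes over the procedure and the significance rule of Testing Hypothesis 2. That procedure fits four count models and allows more than one to be reported if the fit indices disagree. The sample-size section fixes 500 randomized participants (250 per arm) before type 2 exclusions. It gives no power, effect size or variance.

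**The concern.** A single pre-named primary outcome, tested once, needs no multiplicity adjustment to hold its error at 5%. Here the primary and secondary labels have no effect on inference: all three tests are pooled, with no hierarchy, gatekeeping or protected test for H3.

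Two things are at stake. First, the same NSSI data can pass or fail depending on a secondary result. That secondary could be H1, a single 0-4 rating taken straight after a program of about 30 minutes. H3 also inherits the secondaries' open analysis choices, such as linear or ordinal regression for H1. Second, power is lost on the question the trial was set up to answer, and the number randomized is capped at 500.

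**Working it through.** **Inputs from the plan.** Three tests in one FDR family; criterion .05 on the adjusted p value; H3 the sole primary; 1:1 allocation, at most 250 per arm.

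**Assumptions.** The plan gives no power figure, so there is none to reproduce. I take 80% marginal power for H3, with 70% and 90% as a range. I take BH as the procedure. Sidedness is not stated; a coefficient p value plus a required direction is read as two-sided.

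**Step 1: dependence on the secondaries.** This step needs no power assumption. The BH-adjusted p at rank i of 3 is the smallest value of 3 × p(j) / j over j ≥ i.

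| H3 p | Secondary p values | Adjusted H3 p | H3 verdict |
|---|---|---|---|
| .03 | .40, .60 | 3 × .03 / 1 = .09 | not significant |
| .03 | .01, .60 | 3 × .03 / 2 = .045 | significant |
| .03 | .01, .02 | 3 × .03 / 3 = .03 | significant |

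One favorable secondary is enough to change the verdict.

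**Step 2: power at each BH threshold.** The thresholds are .05/3 = .0167, .10/3 = .0333 and .05. Let d = z(.975) + z(power). Power at threshold a is Φ(d − z(1 − a/2)). For 80%, d = 1.960 + 0.842 = 2.802.

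- At .0333: Φ(2.802 − 2.128) = 75.0%.
- At .0167: Φ(2.802 − 2.394) = 65.8%.
- An assumed 70% (d = 2.484) falls at .0167 to Φ(0.090) = 53.6%.
- An assumed 90% (d = 3.242) falls at .0167 to Φ(0.848) = 80.2%.

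**Step 3: power under the full BH procedure.** This was simulated with 1,000,000 trivariate normal draws per scenario and 80% marginal power for H3.

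| Secondaries | Correlation 0 | .3 | .5 |
|---|---|---|---|
| neither has an effect | 66.5% | 66.3% | 66.2% |
| one also powered at 80% | 73.0% | 72.5% | 72.4% |
| both also powered at 80% | 77.6% | 76.8% | 76.4% |

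**Step 4: other readings of the rule.** If Benjamini-Yekutieli were used, 80% would fall to about 58% when neither secondary has an effect. If the p values were one-sided, 80% would fall to about 64% at the strictest threshold.

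**Step 5: type I error for H3.** The most lenient BH threshold is .05, so the error on H3 cannot exceed 5%. In simulation it is 1.8-2.1% under the global null and 5.0% when both secondaries are strongly positive. The worst case therefore equals that of testing H3 alone.

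**Step 6: error after the change.** With H3 tested alone at .05 and BH on H1 and H2, the chance of any positive under a global null with independent tests is 1 − .95 × .95 = 9.75%. At correlation .5 it is just under 9%. Under the present plan it is 4.7-5.0%.

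**The case against.** The case for leaving the plan as it is has weight. All three tests are called confirmatory and one pre-specified rule covers them. Pooling them is permissible, inflates no error and biases no estimate. All of this stands, and it is why the point is an improvement and not a correction of an error.

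Three stronger readings are tempting, and the documents support none of them.

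- A reader might infer that H3's power does fall from 80% to 66%. The plan gives no baseline power and names no FDR procedure. Under BH, 66% is the unfavorable end, where neither secondary has any effect. If both secondaries match H3, the loss is 2-4 points.
- A reader might infer that about a third more participants are needed (334 per arm instead of 250). That figure belongs only to the .0167 threshold, with the same assumed 80%.
- A reader might infer that testing H3 alone guarantees a 5% error rate as the plan stands. It does not. If the fit indices disagree, several models are reported with no rule for which p value decides. A zero-inflated model may also carry a treatment term in more than one part, and the plan does not say which is tested. Lifting the correction without settling this would loosen the criterion on an outcome whose own test is not yet unique.

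A sponsor could also reasonably prefer the tighter control over any false positive. That is a real trade, and its price is in Step 6.

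**Conclusion.** The structural point holds on the text alone: the sole primary outcome has no protected test, and its significance depends on two secondary p values. The choice is valid and conservative.

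The power cost is conditional on BH, two-sided p values and an assumed 80% for H3. It runs from about 2 points (both secondaries equally powered) to about 14 points (neither has an effect). With a different baseline the loss at the strictest threshold is of similar or somewhat smaller size: 70% to about 54%, 90% to about 80%. The point is worth acting on because the remedy is cheap, not because the present rule is wrong.

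**What to change.** Amend Correcting for Multiple Comparisons to say three things.

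1. H3 is tested alone at two-sided .05 and is the sole basis for the primary efficacy claim.
2. A named FDR procedure, for example BH, is applied at .05 to H1 and H2 only.
3. A significant secondary result cannot replace a failed H3.

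In Testing Hypothesis 3, state which single model and which treatment coefficient give the deciding p value. Other selected models can still be reported as sensitivity analyses. The 5% error rate for H3 holds only once this is settled.

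**Cost.** A few sentences and no extra participants; the plan records that no data had been collected. Under a global null the chance of any nominal positive rises from about 5% to 9-10%, while the error of the primary claim stays at no more than 5%. Power for the secondaries changes by roughly a point: about 73% to 72% with one effective secondary, and 77.6% to 78.2% with both, assuming 80% marginal power for each effective test, H3 included.
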